5.5.3. Monitoring of Noninfectious Pneumonitis

Noninfectious pneumonitis has been observed after the administration of MIRV. Noninfectious pneumonitis may result in fatigue, shortness of breath, cough, or respiratory distress. Drug-induced pneumonitis may be immediately life threatening. If a patient presents with signs or symptoms consistent with pneumonitis and/or other clinically meaningful signs or symptoms of pulmonary toxicity, the patient should be immediately evaluated. Patients are advised to notify their treating physician immediately if they experience new or worsening shortness of breath, cough, or respiratory distress. Patients who are asymptomatic may continue dosing of MIRV with close monitoring.

The management and treatment guidelines outlined in [Table 6](#) should be followed.

Document ID: CLIN-00067	Title: IMGN853-0419 Clinical Study Protocol	Version: 2.0
Legacy ID: 26587		Approved Date: 12/22/202

Table 6: Management of Noninfectious Pneumonitis

CTCAE v5.0 Grade	CTCAE v5.0 Definition	Medical Management of Pneumonitis	Guidelines for Dose Modifications ^a
Grade 1	Asymptomatic; clinical or diagnostic observations only; intervention not indicated	
 • Radiologic assessments (CT scan and/or chest x-ray) should be performed as clinically indicated. • Monitor for pulmonary symptoms. 	
 • Continue dosing in asymptomatic patients and monitor closely.
Grade 2	Symptomatic; medical intervention indicated; limiting instrumental ADL	
 • Radiologic assessments (CT scan and/or chest x-ray) should be performed as clinically indicated. • Patient must be evaluated by a pulmonary specialist. • Treatment with corticosteroids may be indicated as recommended by a pulmonary specialist and/or institutional guidelines. 	
 • Hold dosing until symptoms resolve to \leq Grade 1. • MIRV may be resumed at same dose level or one dose level lower after discussion with the Sponsor.
Grade 3	Severe symptoms; limiting self-care ADL; oxygen indicated	
 • Radiologic assessments (CT scan and/or chest x-ray) should be performed as clinically indicated. • Patient must be evaluated by a pulmonary specialist. • Treatment with corticosteroids until resolution of symptoms may be indicated as recommended by a pulmonary specialist and/or institutional guidelines. 	
 • Permanently discontinue MIRV.
Grade 4	Life-threatening respiratory compromise; urgent intervention indicated (eg, tracheotomy or intubation)	
 • Bronchoscopy with lavage and/or biopsy when clinically feasible should be performed. • The pneumonitis event must be followed until resolution. 	

Abbreviations: ADL = activities of daily living; AE = adverse event; CT = computed tomography; MIRV = mirvetuximab soravtansine.

^a Failure to meet retreatment criteria within 1 cycle (21 days) after the missed dose due to insufficient recovery from a treatment-related toxicity will result in treatment discontinuation unless otherwise specified in the management guidance for a particular toxicity.

Document ID: CLIN-00067	Title: IMGN853-0419 Clinical Study Protocol	Version: 2.0
Legacy ID: 26587		Approved Date: 12/22/202

5.5.4. Management of Electrolytes Imbalance

Prompt attention should be given to the correction of potential electrolytes imbalance, especially hypokalemia and hypomagnesemia.

5.5.5. Potential Infusion-related Reactions

Some patients treated with IV infusions of therapeutic drugs have experienced concurrent IRR (see CTCAE Version 5.0). The signs and symptoms may vary and include, for example, headache, fever, facial flushing, pruritus, myalgia, nausea, chest tightness, dyspnea, vomiting, erythema, abdominal discomfort, diaphoresis, shivers, lightheadedness, hypotension, palpitations, and somnolence. Anaphylaxis might occur at any time during an infusion. Before any infusion is started, appropriate medical personnel, medication (eg, epinephrine, inhaled beta agonists, antihistamines, and corticosteroids), and other required resources to treat anaphylaxis must be readily available. In general, Investigators should manage acute allergic or hypersensitivity reactions according to Institutional practices. General guidelines for the management of acute IRRs and for subsequent retreatment are provided in [Table 7](#). Delayed IRRs may occur; therefore, patients should be advised to seek immediate medical treatment if symptoms newly develop and/or recur after discharge from clinic.

Table 7: Management Guidelines for Potential Infusion-related Reactions

Infusion Reaction CTCAE v5.0 Severity Grade	Management
Grade 1: Mild, transient reaction	
 Maintain infusion rate unless progression of symptoms to \geq Grade 2; if symptoms worsen, refer to guidelines below. Promethazine (or equivalent) 150 mg PO per day (Q4h) PRN for nausea Diphenhydramine (or equivalent) 25-50 mg PO or IV PRN Methylprednisolone (or equivalent) 125 mg IV PRN
Grade 2: Moderate	
 Interrupt infusion and disconnect infusion tubing from patient Promethazine (or equivalent) 150 mg PO per day (Q4h) PRN for nausea Diphenhydramine (or equivalent) 25-50 mg PO or IV PRN Acetaminophen (or equivalent) 650 mg PO PRN Methylprednisolone (or equivalent) 125 mg IV PRN After recovery from symptoms, resume the infusion at 50% of the previous rate and if no further symptoms appear, gradually increase rate until infusion is completed. For subsequent dosing in future cycles, patients should be pre-medicated with Dex (or equivalent) 8 mg PO BID the day before drug administration and acetaminophen (or equivalent) 650 mg PO and diphenhydramine (or equivalent) 25-50 mg PO 30-60 min before dosing.
Grade 3: Severe, prolonged reaction not rapidly responsive to symptomatic medication and/or brief interruption of infusion; recurrence of symptoms after initial improvement; hospitalization indicated for clinical sequelae OR Grade 4: Life-threatening consequences, urgent intervention indicated	
 Immediately stop infusion and disconnect infusion tubing from patient. Administer diphenhydramine (25-50 mg) IV (or equivalent) Administer IV steroids (methylprednisolone (or equivalent) up to 0.5 mg/kg Q 6h) to treat ongoing reaction and prevent recurrence Administer bronchodilators (nebulized albuterol/salbutamol, 2.5-5 mg in 3 mL of saline or equivalent) as medically indicated Administer normal saline as medically indicated Administer epinephrine (0.2-0.5 mL of a 1:1000 dilution (0.2-0.5 mg) SQ or IM) as medically indicated. Epinephrine should only be used if all other treatment methods fail to manage the IRR. Advise patient to seek emergency treatment and notify Investigator/clinic if the infusion-related symptoms recur after discharge from clinic. Report as an SAE (see Section 8.1.1.2). Permanently discontinue study medication treatment

Abbreviations: BID = twice a day; CTCAE = common terminology criteria for adverse events; Dex = dexamethasone; IM = intramuscular; IRR = infusion-related reaction; IV = intravenously; PO = orally; PRN = as needed; SAE = serious adverse event; SQ = subcutaneous.

Document ID: CLIN-00067	Title: IMGN853-0419 Clinical Study Protocol	Version: 2.0
Legacy ID: 26587		Approved Date: 12/22/202

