12.7. Protocol Adherence

Each Investigator must adhere to the protocol as detailed in this document and agree that any changes to the protocol must be approved by ImmunoGen's authorized representative in writing before seeking approval, where necessary, from the IRB/IEC, Research Ethics Committee (REC), or Ethics Review Board (ERB). Each Investigator will be responsible for allowing only those patients who have met protocol eligibility criteria to be enrolled.

Modifications to the protocol should not be made without agreement of the Investigators and ImmunoGen. Changes to the protocol will require written IRB/IEC, REC, or ERB approval/favorable opinion before implementation, except when the modification is needed to eliminate an immediate hazard(s) to patients. The IRB/IEC/REC/ERB may provide expedited review and approval/favorable opinion for minor change(s) in ongoing studies that have the approval/favorable opinion of the IRB/IEC/REC/ERB. ImmunoGen will submit all protocol modifications to the appropriate regulatory authorities in accordance with the governing regulations.

When immediate deviation from the protocol is required to eliminate an immediate hazard(s) to patients, the Investigator will contact ImmunoGen, if circumstances permit, to discuss the planned course of action. Any departures from the protocol must be fully documented in the source documentation.

Prospective waivers or exemptions are not permitted.

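### Table 7 makes epinephrine a last resort for Grade 3 and Grade 4 infusion reactions alike, with no exception for life-threatening reactions or anaphylaxis

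*Protocol*

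**What the plan says.** Protocol Section 5.5.5 covers infusion-related reactions (IRRs) and introduces Table 7. It cautions that "Anaphylaxis might occur at any time during an infusion" and requires that "medication (eg, epinephrine, inhaled beta agonists, antihistamines, and corticosteroids), and other required resources to treat anaphylaxis must be readily available". It then says: "In general, Investigators should manage acute allergic or hypersensitivity reactions according to Institutional practices". Its next sentence introduces the table: "General guidelines for the management of acute IRRs and for subsequent retreatment are provided in" Table 7.

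The last row of Table 7 gives one list of actions for Grade 3 or Grade 4. Grade 4 is described there as "Life-threatening consequences, urgent intervention indicated". The epinephrine entry has two sentences. The first reads "Administer epinephrine (0.2-0.5 mL of a 1:1000 dilution (0.2-0.5 mg) SQ or IM) as medically indicated". The second reads "Epinephrine should only be used if all other treatment methods fail to manage the IRR".

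Section 12.7 requires investigators to adhere to the protocol and also provides for emergencies: "When immediate deviation from the protocol is required to eliminate an immediate hazard(s) to patients, the Investigator will contact ImmunoGen, if circumstances permit". The SAP contains nothing on how these reactions are treated. Its Section 7.2.2 only tabulates them.

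**The concern.** The second epinephrine sentence narrows the first. One leaves the drug to the physician's judgement; the other allows it only after everything else has failed. Because the two grades share a cell, the narrower rule also covers a reaction that the row itself calls life-threatening and urgent.

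A site following the cell to the letter could hold back epinephrine in a Grade 4 reaction after the physician has judged it indicated. What is at stake is patient safety during an infusion. No statistical quantity depends on this wording.

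**Working it through.** No arithmetic beyond a count applies, so the check sets the provisions side by side.

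**1. Count of the Grade 3/4 cell.** Leaving out stopping the infusion, patient advice, SAE reporting and discontinuation, the drug and fluid measures are:

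| Measure | Condition in the cell | Extra last-resort limit |
|---|---|---|
| Diphenhydramine IV | none | no |
| IV steroid | none | no |
| Bronchodilators | on medical indication | no |
| Normal saline | on medical indication | no |
| Epinephrine | on medical indication | yes |

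That is 2 unconditional + 3 conditional = 5 measures, of which 1 carries the extra limit. Exceptions written for Grade 4 or anaphylaxis: 0. The bullets are unnumbered and no order of use is given, so the limiting sentence is the only sequencing rule in the cell.

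**2. The limit against the row's own grade definitions.** One element of the Grade 3 definition is a poor or slow response to symptomatic medication or a brief pause in the infusion, so some treatment failure may already be present when a reaction is graded 3. The Grade 4 definition has no such element. Applied literally, the rule therefore asks for failure to be shown first in the grade where urgency is part of the definition.

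**3. What counts as failure.** The cell gives no time limit or criterion, and the reference to all other methods is open-ended. One of those methods, the IV steroid, is dosed every 6 hours. Two repeat drug classes already given: Section 5.4.1 has every patient receive dexamethasone and diphenhydramine, or equivalents, about 30 minutes before each infusion.

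**4. The limit against the text of Section 5.5.5.** The section foresees anaphylaxis and names epinephrine among the example drugs to keep ready for it. Table 7 does not mention anaphylaxis. Applying the limit to anaphylaxis is thus a reading the text permits, not one it states. The Grade 4 conflict in step 2 does not depend on that reading.

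**5. Search for an exception elsewhere.** No other section of the protocol lifts the restriction for Grade 4 or for anaphylaxis.

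**The case against.** The best defence is that Section 5.5.5 already sends anaphylaxis elsewhere. Two consecutive sentences have different subjects: acute allergic or hypersensitivity reactions go to institutional practice, and acute IRRs go to Table 7. The disputed sentence speaks only of managing the IRR. On this reading, anaphylaxis never comes under the limit. The wording is also advisory: it says should rather than must, in a table presented as general guidelines. With no waiting time set, a physician facing a Grade 4 reaction could judge at once that the other methods have failed. Section 12.7 covers departures made to remove an immediate hazard.

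Other provisions make the event less likely:

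- mandatory premedication (5.4.1);
- stepped infusion rates and four hours of observation after the first infusion (5.4.3.1.2);
- exclusion of patients with prior hypersensitivity to monoclonal antibodies or to the study drug (3.1.2).

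The Summary of Changes adds that IRRs have not been common in earlier studies of this drug.

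Much of this stands. It lowers the expected frequency and gives a physician grounds to act early. It does not settle the wording. The split between allergic reactions and IRRs is not explicit: anaphylaxis is raised inside the IRR section, and listed IRR signs such as dyspnea and hypotension could belong to either. A non-allergic Grade 4 reaction stays under the cell on any reading. The deference to institutional practice is general, whereas the epinephrine limit is specific and is what staff would see on opening the table during a reaction. A physician should not have to rely on a deviation clause to give a drug that the preceding sentence allows.

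**Conclusion.** The concern holds as a matter of text. The shared Grade 3/4 cell restricts epinephrine to failure of all other methods, makes no exception for life-threatening reactions or suspected anaphylaxis, and conflicts both with its own row heading and with the sentence before it.

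The instruction is in force at all of the approximately 75 centers, but it acts only on those of the approximately 75 patients who have a Grade 3 or 4 reaction. The documents give no rate for such reactions and no evidence that epinephrine was ever delayed, so the number of patients affected cannot be estimated. The conclusion rests on a literal reading of the cell; delay is a possible consequence, not a demonstrated one. The sponsor should correct the wording. ORR, sample size and error rates are unaffected.

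**What to change.** Delete the last-resort sentence, so that medical indication and institutional anaphylaxis practice govern. If the sponsor wants to keep such a rule, restrict it to Grade 3 reactions that are not suspected anaphylaxis.

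This is a protocol change. Under Section 12.7 it needs written ethics approval before implementation and submission to regulatory authorities. Expedited review is available for minor changes, and the immediate-hazard exception is open if the sponsor considers that it applies. Otherwise the edit can go into the next planned amendment. A short safety memo should go to the approximately 75 centers.

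The cost is one sentence, the amendment paperwork and the memo. No visit, procedure or staff is added. Section 12.8 foresees an amendment or a roll-over study for patients still benefiting at the end of the study, and the sentence should not be carried into either.

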5.5.6. Discontinuation of Mirvetuximab Soravtansine Due to Toxicity

MIRV should be discontinued in the case of the following treatment-related events:

- \geq Grade 3 cardiac event (excluding Grade 3 hypertension) ([Section 5.5.1.1](#))
- \geq Grade 3 pneumonitis event ([Section 5.5.3](#))
- Non-hematologic events of Grade 4 severity ([Section 5.5.1.1](#))
- Ocular events of Grade 4 severity ([Section 5.5.2.2](#))
- Failure to meet re-treatment criteria within 1 cycle (21 days) after the missed dose due to insufficient recovery from a treatment-related toxicity unless otherwise specified in the management guidance for a particular toxicity. In such cases, continuation of MIRV may be considered for those patients who have experienced clinical benefit if agreed upon between the Sponsor and the Investigator.

5.6. Discontinuation of the Patients from the Study or Study Treatment

5.6.1. End of Treatment

Patients will continue to receive MIRV until they present with PD per RECIST v1.1, as assessed by study Investigator, unacceptable toxicity, withdraw consent, or death, whichever comes first, or until the Sponsor terminates the study. Study treatment and/or participation in the study may be discontinued at any time at the discretion of the Investigator. The following may be reasons for the Investigator to remove a patient from the study drug:

- The patient suffers an intolerable AE
- Noncompliance, including failure to appear at one or more study visits
- The patient was erroneously included in the study

The reason for treatment discontinuation must be captured in the clinical trial database. Any AEs experienced up to the point of discontinuation and 30 days thereafter must be documented. All serious adverse events (SAEs), and those AEs assessed by the Investigator as at least possibly related to study drug should continue to be followed until they resolve or stabilize, whichever comes first. Patients will continue to be followed for OS, after discontinuing study drug ([Section 9.3.3](#)).

5.6.2. End of Study

Discontinuation from participation in the study will be documented in the clinical trial database. Reasons for EOS include withdrawal of consent, lost to follow-up, death, or study termination by Sponsor.

5.6.3. Withdrawal of Consent

The patient is free to withdraw consent to study treatment and/or participation in the study at any time irrespective of the reason. The Investigator must make every effort (eg, telephone, email, letter) to determine the primary reason for this decision and record this information. Study

Document ID: CLIN-00067	Title: IMGN853-0419 Clinical Study Protocol	Version: 2.0
Legacy ID: 26587		Approved Date: 12/22/202

treatment must be discontinued, and no further assessments conducted. Further attempts to contact the patient are not allowed unless safety findings require communication or follow-up. If the patient withdraws consent for disclosure of future information, the Sponsor may retain and continue to use any data collected before withdrawal of consent. All biological samples that have been already collected will be retained and analyzed at a later date. The patient may request destruction of any samples, and the Investigator must document this in the site study records. The SAP will specify how early withdrawals from treatment will be accounted for in the analyses of efficacy endpoints. Patients who have withdrawn from the study cannot be re-treated in the study and their inclusion and patient number must not be reused.

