9.2. End of Treatment Visit

Patients may voluntarily withdraw from the study drug at any time for any reason, and without prejudice to further treatment. In addition, patients may be withdrawn by the Investigator if they do not feel the patient is deriving clinical benefit or because the patient is experiencing unacceptable toxicity. The reasons for which a patient may be prematurely discontinued are listed in [Section 5.6](#). The clinical trial database will capture reasons for withdrawal.

Patients who withdraw or are removed from the study treatment will have an EOT visit within 7 days of the decision to discontinue study drug. Patients will undergo assessments as outlined in [Table 2](#).

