9.3.2. Response Follow-up

Patients who discontinued MIRV for reasons other than PD will continue with tumor assessments until documentation of PD or the start of a new anticancer therapy, whichever comes first. Prior to Week 36 (from C1D1), assessments should occur every 6 weeks (\pm 1 week) as allowed by local requirements but must occur at an interval of no more than 12 weeks. After Week 36, assessment will occur every 12 weeks (\pm 3 weeks) until documentation of PD or the start of new anticancer therapy.

Document ID: CLIN-00067	Title: IMGN853-0419 Clinical Study Protocol	Version: 2.0
Legacy ID: 26587		Approved Date: 12/22/202

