9.3.3. Survival Follow-up

All patients who discontinue MIRV for any reason will be followed for survival after PD as per Investigator, or after start of a new anticancer therapy. Survival status will be assessed every 3 months (\pm 1 month) until death, lost to follow-up, withdrawal of consent for survival follow-up, or until EOS, whichever comes first. Additional survival follow-up calls may occur periodically if needed.

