6.1. Efficacy Outcomes

6.1.1. Best Overall Response

Best overall response (BOR) for a patient is the best response designation as assessed by the Investigator recorded between the date of first dose of MIRV and the date of objectively documented PD per RECIST Version 1.1, the date of the start of new anti-cancer therapy, or the date of study discontinuation, whichever occurs first. When an analysis cutoff date is implemented, only radiological assessments occurring on or prior to the cutoff date will be used for analysis. Patients with an overall response of CR or PR must have a repeat tumor assessment performed no less than 4 weeks (28 days) after the criteria for response are first met. When stable disease is the best overall response, it must meet the minimum duration of 35 days (6 weeks – 1 week window = 35 days from the date of first dose of MIRV). The confirmatory scan is valid following treatment discontinuation if the patient has not started a new anti-cancer therapy. Once

a patient has a confirmed response, tumor response may only be recorded as continued response or progressive disease.

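### Protocol 5.6.3 gives withdrawal from study drug the same full stop as withdrawal from the study, in conflict with the follow-up scheduled in 5.6.1, 5.7 and 9.2 to 9.3.3

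*Protocol*

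**What the plan says.** Protocol 5.6.3 states its own scope first: "The patient is free to withdraw consent to study treatment and/or participation in the study at any time irrespective of the reason". The consequence is not divided by what was withdrawn: "treatment must be discontinued, and no further assessments conducted. Further attempts to contact the patient are not allowed unless safety findings require communication". The exception also covers follow-up that safety findings require. The section then leaves it to the SAP to say how early withdrawals from treatment enter the efficacy analyses.

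Elsewhere the protocol treats stopping drug as the start of follow-up:

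- **5.6.1** lists withdrawal of consent among the reasons treatment ends, and then has patients followed for OS after they stop drug.
- **9.2**: "Patients may voluntarily withdraw from the study drug at any time for any reason, and without prejudice to further treatment". Such patients have an End of Treatment visit within 7 days of the decision.
- **9.3.1** sets a visit 30 (+14) days after the last dose.
- **9.3.2**: "Patients who discontinued MIRV for reasons other than PD will continue with tumor assessments until documentation of PD" or a new anticancer therapy begins.
- **9.3.3**: "All patients who discontinue MIRV for any reason will be followed for survival after PD as per Investigator", or after a new therapy starts. One of the listed end points is a withdrawal of consent specific to survival follow-up.
- **5.7** continues scans after drug is stopped without progression, but ends them at an unqualified withdrawal of consent. For survival calls it uses the same specific end point as 9.3.3.

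SAP 6.1.1 expects scans after treatment stops: "The confirmatory scan is valid following treatment discontinuation if the patient has not started a new anti-cancer therapy".

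**The concern.** A patient may want no more infusions and still agree to scans and telephone calls. The opening sentence of 5.6.3 puts her under that section, which ends assessments and contact. Sections 9.2 to 9.3.3 put the same patient into follow-up. Two sites could each follow the protocol and treat her in opposite ways.

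The data at risk feed the primary endpoint (confirmed ORR), the key secondary endpoint (DOR), PFS, OS and the routine post-treatment safety visits. An analysis rule cannot recover scans that were never taken. If the choice to stop is linked to tolerability or lack of benefit, the resulting censoring would be informative. That link is plausible, but the documents do not state it.

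**Working it through.** **Step 1. One patient under both sets of sections.** Suppose a patient has a first PR at the Week 6 scan, then declines further MIRV but accepts follow-up.

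- *Under 9.2 to 9.3.3:* she has an End of Treatment visit within 7 days and a 30-day visit. Scans continue every 6 weeks (±1), at most 12 weeks apart before Week 36, and survival calls follow every 3 months (±1).
- *Under 5.6.3:* none of these takes place, apart from contact that safety findings require.

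No sentence ranks one set above the other.

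**Step 2. What the SAP then does with her data, if 5.6.3 was applied.**

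- *ORR (SAP 6.1.1 and 6.1.1.1):* a response needs a repeat assessment at least 28 days after the criteria are first met. Without it she stays in the denominator and leaves the numerator.
- *DOR and PFS (SAP 6.1.1.2 and 6.1.2):* with no progression or death recorded, she is censored at the last scan. DOR applies only to confirmed responders, so it is affected in those who stop after confirmation.
- *OS (SAP 6.1.3):* she is censored at the last date known alive.
- The SAP has no rule specific to treatment-only withdrawal of consent, although 5.6.3 defers to it.

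**Step 3. Unit effect on ORR.** With 69 efficacy evaluable patients (Protocol 10.1), each response left unconfirmed lowers ORR by 1/69 = 1.45 percentage points. Two decision counts are in play:

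- The two-stage boundary is more than 26 responders, so 27/69 = 39.1%.
- SAP 4.10 requires the Clopper-Pearson lower bound to exceed 28%. The bound is 27.6% at 27/69, which fails, and 28.9% at 28/69 = 40.6%, which passes.

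**Step 4. The plan's own figures.** Inputs from Protocol 10.1: n1 = 28, stop at 9 or fewer responders, n = 69, reject above 26, p0 = 0.28, p1 = 0.48.

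- PET = P(X1 ≤ 9 | 28, 0.28) = 0.7624 (stated 0.762)
- E(N) = 28 + (1 − 0.7624) × 41 = 37.74 (stated 37.74)
- P(reject) = Σ over x1 ≥ 10 of P(X1 = x1) × P(X2 > 26 − x1 | 41, p). This gives 0.0245 at p0 (stated 0.024) and 0.9001 at p1 (stated 0.9).

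The design reproduces, and this point disputes none of its figures.

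**Step 5. Illustration on an assumed loss.** Let w be the share of true responders who lose their confirmatory scan. This is an assumption, because the documents give no value. At a true confirmed ORR of 48%, the expected number of responders is 0.48 × 69 = 33.1, and the observed ORR becomes 0.48 × (1 − w).

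| w | Responders lost of 33.1 | ORR | P(stop at stage 1) | Power |
|---|---|---|---|---|
| 0% | 0 | 0.480 | 0.067 | 0.900 |
| 2% | 0.7 | 0.470 | 0.081 | 0.874 |
| 5% | 1.7 | 0.456 | 0.107 | 0.826 |
| 10% | 3.3 | 0.432 | 0.161 | 0.721 |
| 15% | 5.0 | 0.408 | 0.232 | 0.585 |

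Power here uses the two-stage boundary. SAP 4.10 needs one more responder, so power under that rule would be lower in every row (not computed).

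**The case against.** The best defence is context. Section 9.2 names the patient who leaves study drug voluntarily and gives her a visit, and 9.3.2 and 9.3.3 carry her forward. Section 5.7 distinguishes stopping drug from withdrawing consent. Section 5.6.2 lists withdrawal of consent as a reason for End of Study, and 5.6.3 closes by speaking of patients who have left the study. On that reading the full stop belongs to study withdrawal, and the defect is a loose conjunction in one sentence.

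This narrows the point but does not remove it. The first sentence of 5.6.3 names study treatment, and its deferral to the SAP concerns withdrawals from treatment. It is the section titled for withdrawal of consent, so a site would naturally consult it. Sections 4.1.1 and 5.7 also end scans at an unqualified withdrawal of consent, which does not help the site decide.

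Several limits do stand:

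- **Not every patient who stops by choice is affected.** A reader might infer that the design discards follow-up for all of them. The documents do not support that, because loss arises only where a site applies 5.6.3 over 9.2 to 9.3.3.
- **The ORR window is narrow.** A response is lost only if the patient stops between first response and confirmation. Stopping after confirmation leaves ORR unchanged.
- **The ORR error is conservative.** It lowers ORR and cannot create a false positive.
- **Safety data are not wholly lost.** Section 5.6.3 keeps safety-driven contact. Section 5.6.1 requires AEs to be documented for 30 days after discontinuation, and SAEs and related AEs to be followed until they resolve or stabilise. The routine visits are what is at risk.
- **Some toxicity-driven stops would not come under 5.6.3.** Unacceptable toxicity is a separate reason for ending treatment in 5.6.1.

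**Conclusion.** The inconsistency is real on the plain wording and should be corrected. Section 5.6.3 states a rule that, applied literally, cancels assessments and calls that other sections schedule for the same patient.

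The only size the documents support is per patient: 1.45 percentage points of ORR for each responder who stops by choice before confirmation, at a site that follows 5.6.3. It is tempting to turn this into a patient count by assuming a withdrawal rate. The documents give no such rate, nor the share of sites that would follow 5.6.3, nor the share of withdrawals falling in the confirmation window. The power table therefore shows sensitivity only and is not a forecast.

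For DOR, PFS and OS the direction of any bias is unknown. It depends on whether patients who decline further drug would have progressed or died sooner or later than those who stay under observation.

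**What to change.** Reconcile the passages in a protocol amendment:

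1. In 5.6.3, limit the instruction "treatment must be discontinued, and no further assessments conducted" and the contact ban to full withdrawal from the study, keeping the safety exception.
2. State that withdrawal from study treatment only leads to the End of Treatment visit, 30-Day Follow-up, response follow-up and survival follow-up already set out in 9.2 to 9.3.3.
3. For any other partial withdrawal, stop only the component withdrawn: scans and visits, or survival follow-up.
4. Have sites record which level was withdrawn. SAP 5.2.2 already uses separate End-of-Treatment and End-of-Study forms, so this may need only one added field.
5. Align the unqualified withdrawal wording in 4.1.1 and 5.7 (and the matching synopsis text), and add the corresponding rule to the SAP, as 5.6.3 promises.

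The cost is a few sentences, the IRB/IEC approval that Protocol 12.7 requires for protocol changes, and slightly more follow-up work at sites. No new visit or procedure is needed, because all are already scheduled for patients who stop MIRV.
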